3.7.6 Augmented reality serious games (ARSG)

FrailSafe will rely on the augmented reality (AR) gaming concept offering both clinical assessment and rehabilitation options, usually not available with traditional rehabilitation methods. It aims exploiting vision technologies to provide older people with assistive visual

feedback while performing games/rehabilitation as well as medical staff with biomechanic indicators for assessment and diagnosis support. Moreover, the AR gamer environment motivates the individual and makes him/her train more often and for a longer period of time without getting tired. The continuous feedback provided by the AR therapeutic programs builds and strengthens his/her motivation.

The AR glasses will provide to the study participants the opportunity to test the augmented reality serious games (ARSG) for both diagnostic and maybe therapeutic reasons. In contrast to VR, AR superimposes a computer-generated image on a user's view of the real world. The interest lies in the fact that we can close the loop between interventions and behavioral measurements. So by using a game where walking on a synthetic red line on the carpet will be demanded, measurements of instabilities and gait properties will be performed. At the same time, the idea is to create a navigation AR game that will motivate the older adults to increase their mobility by setting goal-driven scenarios such as short-distance (walk to the wall) and long-distance ones (follow the 'virtual' line for 100 meters).

The AR glasses will be delivered by the nurses during the FrailSafe system home visit and explication of their use and objective will be given. Training for ARSG playing will also be handled by the nurses, as well as assistance during the standing mobility challenges. Additionally, a training application will be provided where the user will look around and investigate virtual objects. In the case of seated alternatives of these games, individual training as often as possible will be encouraged.

Although the use of the AR glasses was described since the begging of the study, their actual feasibility of use by this study's participants and under given conditions, is still an issue of discussion and reflexion among the Consortium.

3.7.7 FrailSafe system experience satisfaction interview

At the end of each FrailSafe system home visit a short interview of satisfaction is administered to each participant. The aim is to test the FrailSafe system's ease of use, identify any practical difficulties the participant experienced in its handling in the home settings and evaluate the individual's acceptance. The participants' remarks will be taken into account for the developing and amelioration of the FrailSafe system.

3.7.8 FrailSafe system's application standardization

As predicted by the initial proposal and its amendments, not the totality of the FrailSafe system devices was available since the beginning of the clinical study.

Therefore, we noted a quite important heterogeneity among the first FrailSafe sessions conducted in the centres of Patras and Cyprus. In order to address this source of bias, the

very first participants for whom the FrailSafe session was incomplete according to some minimum requirements (enlisted bellow), will be called back in order to repeat the session.

The FraiSafe system devices which are currently available and are going to be used in all FraiISafe sessions (=home visits), from now until new versions of devices arrive, are:

- The tablets with virtual reality games (for all participants)
- The smartphones with the GPS application (for all participants)
- The blood pressure monitoring devices (for all participants)
- The WWS devices (strap version) (for 1 participant at a time)
- The dynamometers for grip strength games' playing (for all participants)
- The beacons (for all participants).

Towards the direction of standardizing the procedures and adapting the material to the actual needs of the participants, working documents treating practical issues such as study's material, anticipated and actually occurring problems and procedures have been generated and are being constantly updated. Similarly, detailed check lists about the material, requirements and conditions to be verified before, during and after the clinical evaluation and the FrailSafe home visits have been distributed in the 3 clinical centres (Annex 19).

4. Operational procedures per group

In a more concentrated and systematic way the operational procedures per group are as following:

4.1 All groups

- 1. Quick first verification of inclusion and exclusion criteria
- 2. Randomization to groups (only applicable for group C and D)
- 3. Informed consent and attribution of a unique ID number
- 4. First part of clinical evaluation session: questionnaires to verify inclusion and not inclusion criteria, Fried's criteria of frailty, medical history and cognitive assessment will be administered (tables 4, 5, 6, 9, 13).
- 5. Second verification of the inclusion/exclusion criteria according to the first part of the clinical evaluation's results. If exclusion, replacement of the participant and repetition of steps 1-5 for the next candidate

The steps from this point down and their time programming will differ according to group allocation.

4.2 Group A- Start Up group:

- 1-5. As described above for all groups
- 6. Complete clinical evaluation session (tables 7, 8, 10, 11, 12, 14) (M≥6)
- 7. Data collection regarding social interaction and natural language analysis:
 - Data collection of written text for the first time (table 15), where the participant will either be helped to provide text by dictation or be asked to prepare it him/herself in his/her home and deliver it to us in the next appointment and
 - self-administered questionnaires The Social Media (annex 16) and the Big five (annex 17) questionnaire will be given to participants in order to fill them in themselves and deliver them to us in the next appointment
- 8. First FrailSafe system home visit (M≥6):
 - Blood sampling for telomeres
 - Fill in the evaluation form regarding the participant's housing (table 18)
 - Collect any questionnaires filled in by the participant since the last visit: written texts, social media and big five questionnaires
 - Complete any missing information of the clinical evaluation (i.e. scanning of a forgotten prescription, scanning of an older written text provided by the participant, write down dictated text)
 - Installation of the currently available FrailSafe system and explication of the use, the purposes and the technical issues of the FrailSafe material. Verification of its correct function
 - Provide contact details and instructions in case of any help needed
 - Set the next appointment to retrieve the FrailSafe material (5th day)
- 9. Maintenance of the FrailSafe system at home during 3-5 days
- 10. Daily phone calls during the instauration of the FrailSafe system to catch up with the experience of the use of the material and any problems that may have arisen
- 11. Short satisfaction interview in the day of FrailSafe system retrieval
- 12. Telephone Follow-up after the retrieval of the FrailSafe in a 3 months' basis (table 17). (M9-M24)
- 13. Second clinical evaluation (M27) (tables 5-14)
- 14. Data collection of written text after the first time (table 16) (M27). The participant will either be helped to provide text by dictation or be asked to prepare it him/herself in his/her home and deliver it to us in the next appointment
- 15. Second FrailSafe system instauration (M27)
 - [Only for Patras]: blood sampling
 - Fill in the evaluation form regarding the participant's housing (table 18)
 - Collect any questionnaires filled in by the participant since the last visit (written texts)

- Complete any missing information of the clinical evaluation (i.e. scanning of a forgotten prescription, scanning of an older written text provided by the participant, write down dictated text)
- Administration of follow up questionnaire (table 17)
- Installation of the currently available FrailSafe system and reminding of the use, the purposes and the technical issues of the FrailSafe material (Session 3.8). Verification of its correct function
- Provide contact details and instructions in case of any help needed
- Set the next appointment to retrieve the FrailSafe material (5th day)
- 16. Maintenance of the FrailSafe system at home during 3-5 days
- 17. Daily phone calls during the instauration of the FrailSafe system to catch up with the experience of the use of the material
- 18. Telephone Follow-up after the second retrieval of the FrailSafe (M30) (table 17)
- 19. Last clinical evaluation (M33) (tables 5-14)
- 20. Data collection of written text after the first time (table 16) (M33). The participant will either be helped to provide text by dictation or (s)he will write it down during the clinical assessment appointment
- 21. Last telephone follow up M36
- 22. Study's completion verification (table 20). Normally at the end (M36), but could be in anytime in case of premature withdrawal.

Did the patient complete the study as predicted?	1. Yes 2. No
If no, provide the reason for the premature ending of his/her participation	 Death Consent withdrawal Emerging condition inhibiting the participation in the study or fulfilling exclusion criteria Participant unreachable/ Lost in follow up

Table 20. STUDY'S COMPLETION VERIFICATION

This option will be provided to fill in by the investigator once in each patient's dataset, in the end of his/her participation, whether this corresponds to a completion of the study as predicted or to a premature withdrawal

4.3 Group B- Main group:

- 1-5. As described above for all groups
- 6. Complete clinical evaluation session (tables 7, 8, 10, 11, 12, 14) (M10)
- 7. Data collection regarding social interaction and natural language analysis:
 - Data collection of written text for the first time (table 15), where the participant will either be helped to provide text by dictation or be asked to prepare it him/herself in his/her home and deliver it to us in the next appointment and
 - self-administered questionnaires The Social Media (annex 16) and the Big five (annex 17) questionnaire will be given to participants in order to fill them in themselves and deliver them to us in the next appointment
- 8. First FrailSafe system home visit (M10):
 - Blood sampling for telomeres
 - Fill in the evaluation form regarding the participant's housing (table 18)
 - Collect any questionnaires filled in by the participant since the last visit: written texts, social media and big five questionnaires
 - Complete any missing information of the clinical evaluation (i.e. scanning of a forgotten prescription, scanning of an older written text provided by the participant, write down dictated text)
 - Installation of the currently available FrailSafe system and explication of the use, the purposes and the technical issues of the FrailSafe material (Session 3.8). Verification of its correct function
 - Provide contact details and instructions in case of any help needed
 - Set the next appointment to retrieve the FrailSafe material (5th day)
- 9. Maintenance of the FrailSafe system at home during 5 days
- 10. Daily phone calls during the instauration of the FrailSafe system to catch up with the experience of the use of the material and any problems that may have arisen
- 11. Short satisfaction interview in the day of FrailSafe system retrieval
- 12. FrailSafe system home visit (M12)
 - Administration of follow up questionnaire (table 17)
 - Installation of the currently available FrailSafe system and reminding of the use, the purposes and the technical issues of the FrailSafe material. Verification of its correct function
 - Provide contact details and instructions in case of any help needed
 - Set the next appointment to retrieve the FrailSafe material (5th day)
- 13. Maintenance of the FrailSafe system at home during 3-5 days
- 14. Daily phone calls during the instauration of the FrailSafe system to catch up with the experience of the use of the material and any problems that may have arisen
- 15. Short satisfaction interview in the day of FrailSafe system retrieval

- 16. Repetition of steps 12-15 for a total of 7 FrailSafe system home visits (M12-M27) every 2 months (with the exception of the first three to be conducted in an interval of 3 months (section 2.6).
- 17. Second clinical evaluation (M16) (tables 5-14)
- 18. Data collection of written text after the first time (table 16) (M16). The participant will either be helped to provide text by dictation or be asked to prepare it him/herself in his/her home and deliver it to us in the next appointment
- 19. Third clinical evaluation (M22)
- 20. Data collection of written text after the first time (table 16) (M22). The participant will either be helped to provide text by dictation or be asked to prepare it him/herself in his/her home and deliver it to us in the next appointment
- 21. [Only for Patras]: Second blood sampling (M25)
- 22. Last FrailSafe system home visit (M26). As in steps 12-15 with the addition of:
 - Fill in the evaluation form regarding the participant's housing (table 18)
- 23. Two telephone follow-ups after the last retrieval of the FrailSafe (M29 andM32) (table 17)
- 24. Last clinical evaluation (M35) (tables 5-14)
- 25. Data collection of written text after the first time (table 16) (M35). The participant will either be helped to provide text by dictation or (s)he will write it down during the clinical assessment appointment.
- 26. Study's completion verification (table 20). Normally at the end (M36), but could be in anytime in case of premature withdrawal.

By following this methodology for groups A and B a considerable amount of continuous data from a large number of participants will be recorded, minimizing the impact of the relatively small number of equipments. It is believed that monitoring these older people, especially of group B, every two months, very little information regarding changes and transition of frailty will be missed. By this time, significant development and many amelioration to the technical aspects of the FrailSafe system is expected to have been achieved.

4.4.1 Group Ci- Standard evaluation group:

- 1-5. As described above for all groups
- 6. Complete clinical evaluation session (tables 5, 7, 8, 10, 11, 12, 14) (M31)
- 7. First FrailSafe system home visit (M31):
 - Blood sampling for telomeres
 - Fill in the evaluation form regarding the participant's housing (table 18)
 - Collect any questionnaires filled in by the participant since the last visit: written texts, social media and big five questionnaires

- Complete any missing information of the clinical evaluation (i.e. scanning of a forgotten prescription, scanning of an older written text provided by the participant, write down dictated text)
- Installation of the currently available FrailSafe system and explication of the use, the purposes and the technical issues of the FrailSafe material. Verification of its correct function
- Provide contact details and instructions in case of any help needed
- Set the next appointment to retrieve the FrailSafe material (5th day)
- 8. Maintenance of the FrailSafe system at home during 5 days
- 9. Short satisfaction interview in the day of FrailSafe system retrieval
- 10. FrailSafe system home visit (M33)
 - Administration of follow up questionnaire (table 17)
 - Installation of the currently available FrailSafe system and reminding of the use, the purposes and the technical issues of the FrailSafe material (Session 3.8). Verification of its correct function
 - Provide contact details and instructions in case of any help needed
 - Set the next appointment to retrieve the FrailSafe material (5th day)
- 11. Maintenance of the FrailSafe system at home during 5 days
- 12. Short satisfaction interview in the day of FrailSafe system retrieval
- 13. Last FrailSafe system home visit (M35). Repetition of steps 12-15.
- 14. [Only for Patras]: Second blood sampling (M35)
- 15. Last clinical evaluation (M36) (tables 5-14)
- 16. Data collection of written text after the first time (table 16) (M36). The participant will either be helped to provide text by dictation or (s)he will write it down during the clinical assessment appointment.
- 17. Study's completion verification (table 20). Normally at the end (M36), but could be in anytime in case of premature withdrawal.

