2.2 Participants' characteristics

The Clinical study will be performed in 3 Clinical Centers: University of Patras (UoP), Greece; INSERM-Nancy, France; and MATERIA- Nicosia, Cyprus. Each Center will recruit 170 individuals for the FrailSafe study. By this way a total of 510 community living subjects aged 70 years and older will be recruited. The inclusion and non-inclusion criteria are demonstrated in table 1.

Table 1. Inclusion and exclusion criteria

Inclusion criteria
Age ≥70 years
Informed consent provided
Exclusion criteria
Lack of wish to participate
Consent withheld
Inability to give consent because of incapacity
Inability to walk
Inability to speak Greek or French (see clinical centers)
Diagnosis of clinically significant cognitive impairment or score less than 24 on the Mini– Mental State Examination
Diagnosis of advanced malignancy, other terminal illness or an estimated life expectancy of less than 12 months
Active psychiatric disorder based on medical records or clinical opinion at the time of recruitment, current substance users, or excessive alcohol drinkers.

The numerical threshold for "older age" has always been controversial, though most widely accepted was the age of 65 years, corresponding in the usual age of retirement. Still, nowadays "young old" individuals maintain a good general health condition and with the exception of special cases, frailty is most likely to be encountered in older age ranges. In the FrailSafe study, since we need to include people in non-frail, pre-frail, as well as frail conditions, it was decided that the age threshold will be that of 70 years.

In order to be able to comply better with the requirements of the study (usage of technical material, cooperation for the testing of novel equipment, need for participant's feedback and relatively long follow up period), subjects with highly debilitating conditions, such as inability to walk, presence of clinically significant cognitive impairment, or active psychiatric

disorder will be excluded from the study. Similarly, subjects with serious medical conditions that convey a guarded prognosis (estimated life expectancy of less than 12 months) will be excluded as well.

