3.1.10 Assessment subset 10: Cognitive, mood and sleep evaluation

This session includes the following parts:

Global cognitive function evaluation. The Mini Mental State Examination (MMSE) test is employed (23), (annex 8), available in translated and validated versions in both French and Greek (24, 25). This scale is the most widely used instrument of global assessment of cognitive function both in clinical, epidemiological and research settings. It is useful as a screening tool in order to detect a cognitive dysfunction and to follow up its evolution, but it lacks specificity to distinguish between certain forms of dementia and sensitivity to discriminate a mild dysfunction in an early stage (26). Moreover it is highly influenced by the age and educational level (27, 28). A cut off score of below 24 during the first evaluation is used as an exclusion criterion for the present study, in order to avoid recruiting participants with important cognitive problems who are less likely to be able to use in an optimal way the FrailSafe system's devices and applications and to be apt for the follow up period.

To overcome the inherent inability of MMSE to detect more discreet cognitive dysfunctions and to augment the sensitivity of cognitive testing in highly educated older adults, the Montreal Cognitive Assessment (MoCA, annex 9) is also employed. The latter is a brief cognitive screening tool for the detection of MCI (29, 30, 31), available in multiple languages, among which the French and Greek. Since MCI is an important morbidity for our study, this scale will contribute to its detection.

- Memory complaint's detection. The expression of a memory complain from an older subject could be an indication of early sings of cognitive dysfunction (32), although there is not global consistency in this finding in the literature (33). Still, the general tendency is that subjective memory complains merit further evaluation (34, 35).
- Depression screening. The 15-items' Geriatric Depression Scale (GDS) (36) (annex10) is used in order to detect subjects with possible depression. This scale cannot pose the definitive diagnosis of depression, even though there is some evidence that it can detect a major depressive episode (37). Still it can be used to screen for depressive symptoms (38). It is available in both Greek in a validated version (39) and in French (40).

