5.2.2 Proxy outcomes

Due to the limited number of participants, the tight timeframe of the project and the frequency of occurrence of Hard Outcomes, we propose the use of proxy outcomes that we are confident that we will be able to measure and to use in the data analysis part of the project to draw some solid conclusions. The proxy outcomes could also be considered as a diagnostic, early detection tool of a declining condition that may lead to a hard outcome. By keeping a concise, short, practical yet informative track of the change in proxy outcomes we will be able via coaching and interventions to postpone the inevitable occurrence of a Hard outcome, thus improving prognosis and quality of life.

Repeated clinical evaluations are carried out in the following domains: physical, cognitive, psychological, nutritional, and wellness. Loss of function in each domain can indirectly describe loss of physiological reserve, which underscores frailty, and consequently the adverse events of frailty (described above in 5.2.1). The clinical experts of this consortium in a consensus meeting have agreed on a key clinical assessment of each domain, which best describes loss of reserve and is believed to predict adverse outcome.

Therefore, as proxy outcomes have been selected the following:

- Gait speed (Physical Domain)
- MoCA and/or MMSE (Cognitive Domain)
- GDS (Psychological Domain)
- Weight loss (Nutritional Domain)
- Health status self-assessment (General health/Wellness Domain)

The clinicians in the process of selecting a proxy outcome in each domain made use of the bibliography and their expert opinion. At the end of the clinical studies, analysis will be carried out correlating these proxy outcomes to the hard outcomes observed in participants and, if possible, explore validity and reliability.

Review of the bibliography showed that gait speed test has been established as the test with the strongest correlation to frailty (72), and has been linked with the hard outcomes, such as falls and mortality (73,74). Reduced MoCA and MMSE scores, though the later to a lesser extent as less sensitive to the detection of mild cognitive decline, have been linked both with

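### Table 20 and Section 3.1.3 allow exit for meeting an exclusion criterion during follow-up, although other sections apply these criteria only at entry; taken literally, dropout then depends on the outcomes

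*Protocol*

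**What the plan says.** Table 20 is printed in Section 4.2 and is the closing step for every group in Sections 4.2 to 4.5. If the study was not completed, the investigator must "provide the reason for the premature ending of his/her participation". One of the four answers is "Emerging condition inhibiting the participation in the study or fulfilling exclusion criteria". On timing, the step reads "Normally at the end (M36), but could be in anytime in case of premature withdrawal".

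The criteria are in Table 1 (Section 2.2). They include "Inability to walk", "Diagnosis of clinically significant cognitive impairment or score less than 24 on the Mini" (the Mini-Mental State Examination) and "Diagnosis of advanced malignancy, other terminal illness or an estimated life expectancy of less than 12 months". Table 1 itself sets no time limit. Section 3.1.3 adds that a person is excluded if an active psychiatric disorder, a terminal condition or substance abuse emerges from the history, again without saying when. That history (Table 6) is taken again at later evaluations, which use Tables 5 to 14.

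Other sections point to entry only. Section 3.1 verifies eligibility in the first part of the first evaluation. Section 4.1 has two checks, steps 1 and 5, both before the group-specific schedule begins. Section 3.1.10 says: "A cut off score of below 24 during the first evaluation is used as an exclusion criterion for the present study".

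Section 2.5 provides for exit on withdrawal of consent, death or a condition that makes participation impossible. The proxy outcomes in Section 5.2.2 include gait speed and MoCA and/or MMSE. The hard outcomes in Section 5.2.1 include unplanned hospitalisation, institutionalisation, death and decline in ADL or IADL.

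**The concern.** The word *emerging* places the Table 20 reason after entry, and the *or* makes meeting an exclusion criterion sufficient even for someone still able to take part. Three exclusion criteria (walking, cognition, prognosis) lie on the same axes as study outcomes (gait speed, MoCA/MMSE, death). A centre that follows Table 20 or Section 3.1.3 to the letter can therefore close a participant's record because of the deterioration that the study sets out to describe and predict.

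At stake are the later course of the proxy outcomes and the hard outcomes after exit, in people likely to have them. Sections 5.2.2 and 5.4.2.3 already concede that hard outcomes will be few. The analyses exposed are those linking the indices to outcomes (MO2 to MO5 in Table 24). Centres that read the passages differently would also lose different kinds of participants.

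**Working it through.** The protocol states no dropout rate, event rate or effect size for this point, so there is no figure to reproduce. The check sets the passages side by side.

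**1. Which criteria can act after entry?**
- *Walking:* in Table 1 without a time limit. Section 4.1 checks it at entry; Table 20 reopens it.
- *Cognitive impairment by diagnosis:* the same position.
- *MMSE below 24:* reopened by the wording of Table 20, but Section 3.1.10 ties it to the first evaluation. The two conflict.
- *Terminal illness or short prognosis:* Section 3.1 places it in the first evaluation. Section 3.1.3 has no limit, and Table 20 reopens it.

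**2. What is kept and what is lost?** A finding must be recorded before it can lead to exit, so the value at the triggering visit is in the data, as is a death during participation. After exit, no section continues the Table 17 calls, the ADL/IADL follow-up or vital status. A death after exit for terminal illness would not be captured.

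**3. Effect on the trajectory model.** Section 5.2.2 fits f(t) = a − b·t − c·t² and sets c to zero with fewer than three time points.
- *Group A:* entry, M27 (M26 in Section 2.5) and M33 make 3 evaluations. Exit at the second leaves 2, so c = 0. The M30 call, the M33 evaluation and the M36 call are lost.
- *Group B:* M10, M16, M22 and M35 make 4. Exit at M16 leaves 2, so c = 0. Exit at M22 leaves 3, but the following 35 − 22 = 13 months up to the last evaluation are unseen.
- *Groups C and D:* M31 and M36 make 2, so c = 0 for everyone. Exit before M36 leaves 1 and no change score. Table 17 contains no MMSE, so a low repeat MMSE can first appear at M36, when the change score already exists.

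**4. Effect on the other analyses.** The Cox model named in Section 5.2.2 assumes that, given the covariates, censoring is unrelated to the risk of the event. Exit for lost walking or terminal illness breaks that assumption. Section 5.4.1 reconstructs missing parts from models learned on complete data, which here come from those who stayed.

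**5. Illustration of direction only; every input is assumed.** The one route with a numerical threshold is MMSE below 24, which Section 3.1.10 limits to entry. If a centre nevertheless applied it at group A's second evaluation, the times from entry at M6 would be 27 − 6 = 21 and 33 − 6 = 27 months. The model is MMSE(t) = baseline + slope·t + error, rounded and capped at 30. The underlying baseline has mean 27 and SD 1.8, entry requires an observed score of at least 24, and exit follows a score below 24 at 21 months.

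| Slope per year, mean (SD) | Error SD | Leave | Mean change to 27 months, everyone | Those retained |
|---|---|---|---|---|
| −0.3 (0.5) | 1.0 | 6.9% | −0.72 | −0.63 |
| −0.5 (1.0) | 1.0 | 14.4% | −1.23 | −0.82 |
| −0.5 (1.0) | 1.5 | 16.2% | −1.32 | −0.88 |
| −1.0 (1.5) | 1.5 | 28.8% | −2.48 | −1.25 |

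In all four cases the retained group declines less than the full cohort. This shows the direction of the effect on that reading. It does not estimate the bias in this study and says nothing about the walking, diagnosis or prognosis routes.

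**The case against.** The strongest reply is that Table 20 is a form completed once participation has ended. It records why someone stopped and instructs nobody to stop. The operative exit text, Section 2.5, requires that participation be impossible. No step in Sections 4.2 to 4.5 re-applies Table 1 after entry. The forms expect people who decline to stay: Table 8 allows a test that cannot be done, Table 9 allows an inadequate gait test, Table 17 records worsening and institutionalisation, and texts may be dictated.

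Much of this stands. There is no scheduled withdrawal rule. A reader might infer that anyone who enters at MMSE 25 and later scores 23 must leave; Section 3.1.10 contradicts that. A reader might also infer that low MMSE scores distort the comparison of groups C and D. They cannot act before M36, so any such effect runs only through new walking loss, diagnosis or prognosis between M31 and M36. Nor can it be said that participants with mild cognitive impairment are affected most, since the protocol gives no MMSE distribution by MCI status.

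The reply does not explain why the form separates fulfilling a criterion from being unable to take part. Nor does it supply the entry limit missing from Section 3.1.3, or any sentence that continues follow-up.

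**Conclusion.** The point holds as a conflict within the protocol. Table 20 and Section 3.1.3 permit exit on a criterion met during follow-up, whereas Sections 3.1, 3.1.10 and 4.1 confine the criteria to entry. On the literal reading, dropout depends on the outcomes. The later trajectory and later hard outcomes are lost, and censoring is informative for the Cox and index-outcome analyses. The walking and diagnosis routes rest on Table 20 alone; the prognosis route rests on both passages.

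The conclusion assumes that at least some centres act on the literal wording and that an exit ends all contact, since nothing says otherwise. The size cannot be derived from the documents. It depends on how many exits are coded to this reason because a criterion was met rather than because participation was impossible, and the form merges the two. A comparison that discards the score at the triggering visit would overstate the loss.

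**What to change.** Reconcile the passages before further exits are coded:

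- In Table 20, delete the words on fulfilling exclusion criteria and keep the reason of a condition that prevents participation.
- In Section 2.2, state that Table 1 applies only at the two entry checks (Section 4.1, steps 1 and 5), and give the exclusion sentence in Section 3.1.3 the same limit.
- Record the end of device sessions separately from the end of study follow-up. Whether device use should stop for a given person is a clinical matter on which this point takes no position.
- For anyone who later meets a Table 1 criterion, and subject to consent, continue the scheduled clinical evaluations where feasible and the Table 17 and ADL/IADL follow-up to M36.

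The cost is one line in Table 20, one sentence each in Sections 2.2 and 3.1.3, and one extra field on the form. The visits and calls are already in the schedule. The downside is that some later evaluations will be partial or by telephone. Follow-up that was never collected cannot be recovered by a later analysis.
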